Appendix 10: Mindful Attention Awareness Scale

Day-to-Day Experiences

Instructions: Below is a collection of statements about your everyday experience. Using the 1-6 scale below, please indicate how frequently or infrequently you currently have each experience. Please answer according to what *really reflects* your experience rather than what you think your experience should be. Please treat each item separately from every other item.

| | | | | | |
|------------------|-----------------|------------------------|--------------------------|----------------------|-----------------|
| 1 | 2 | 3 | 4 | 5 | 6 |
| Almost Always | Very Frequently | Somewhat Frequently | Somewhat Infrequently | Very Infrequently | Almost Never |

| | | | | | | |
|--------------------------------------------------------------------------------------------------------------|---|---|---|---|---|---|
| I could be experiencing some emotion and not be conscious of it until some time later. | 1 | 2 | 3 | 4 | 5 | 6 |
| I break or spill things because of carelessness, not paying attention, or thinking of something else. | 1 | 2 | 3 | 4 | 5 | 6 |
| I find it difficult to stay focused on what's happening in the present. | 1 | 2 | 3 | 4 | 5 | 6 |
| I tend to walk quickly to get where I'm going without paying attention to what I experience along the way. | 1 | 2 | 3 | 4 | 5 | 6 |
| I tend not to notice feelings of physical tension or discomfort until they really grab my attention. | 1 | 2 | 3 | 4 | 5 | 6 |
| I forget a person's name almost as soon as I've been told it for the first time. | 1 | 2 | 3 | 4 | 5 | 6 |
| It seems I am "running on automatic," without much awareness of what I'm doing. | 1 | 2 | 3 | 4 | 5 | 6 |
| I rush through activities without being really attentive to them. | 1 | 2 | 3 | 4 | 5 | 6 |
| I get so focused on the goal I want to achieve that I lose touch with what I'm doing right now to get there. | 1 | 2 | 3 | 4 | 5 | 6 |
| I do jobs or tasks automatically, without being aware of what I'm doing. | 1 | 2 | 3 | 4 | 5 | 6 |
| I find myself listening to someone with one ear, doing something else at the same time. | 1 | 2 | 3 | 4 | 5 | 6 |
| I drive places on 'automatic pilot' and then wonder why I went there. | 1 | 2 | 3 | 4 | 5 | 6 |
| I find myself preoccupied with the future or the past. | 1 | 2 | 3 | 4 | 5 | 6 |
| I find myself doing things without paying attention. | 1 | 2 | 3 | 4 | 5 | 6 |
| I snack without being aware that I'm eating. | 1 | 2 | 3 | 4 | 5 | 6 |

Scoring: To score the scale, simply compute a mean (average) of the 15 items. Higher scores reflect higher levels of dispositional mindfulness.

Curiosity and Exploration Inventory-II

| Curiosity and Exploration Inventory (CEI-II) | | Very Slightly or Not at all | A Little | Moderately | Quite a Bit | Extremely |
|----------------------------------------------------------------------------------------------------------------------------------------------------------------------------------------------------------------------------------------------|--------------------------------------------------------------------------------------------|-----------------------------|----------|------------|-------------|-----------|
| Instructions: Rate the statements below for how accurately they reflect the way you generally feel and behave. Do not rate what you think you should do, or wish you do, or things you no longer do. Please be as honest as possible. | | | | | | |
| 1. | I actively seek as much information as I can in new situations. | 1 | 2 | 3 | 4 | 5 |
| 2. | I am the type of person who really enjoys the uncertainty of everyday life. | 1 | 2 | 3 | 4 | 5 |
| 3. | I am at my best when doing something that is complex or challenging. | 1 | 2 | 3 | 4 | 5 |
| 4. | Everywhere I go, I am out looking for new things or experiences. | 1 | 2 | 3 | 4 | 5 |
| 5. | I view challenging situations as an opportunity to grow and learn. | 1 | 2 | 3 | 4 | 5 |
| 6. | I like to do things that are a little frightening. | 1 | 2 | 3 | 4 | 5 |
| 7. | I am always looking for experiences that challenge how I think about myself and the world. | 1 | 2 | 3 | 4 | 5 |
| 8. | I prefer jobs that are excitingly unpredictable. | 1 | 2 | 3 | 4 | 5 |
| 9. | I frequently seek out opportunities to challenge myself and grow as a person. | 1 | 2 | 3 | 4 | 5 |
| 10. | I am the kind of person who embraces unfamiliar people, events, and places. | 1 | 2 | 3 | 4 | 5 |
| Stretching: 1, 3, 5, 7 / Embracing: 2, 4, 6, 8, 10. | | | | | | |

University Rhode Island Change Assessment Scale (URICA)

Each statement below describes how a person might feel when stating therapy or approaching problems in his life. Please indicate the extent to which you tend to agree or disagree with each statement. In each case, make your choice in terms of how you feel right now, not what you have felt in the past or would like to feel. For all the statements that refer to your "problem", answer in terms of problems related to substance use and/or mental health. The words, "here" and "this place" refer to your treatment center.

There are five possible responses to each of the items in the questionnaire:

1=Strongly Disagree

2=Disagree

3=Undecided

4=Agree

5=Strongly Agree

Circle the number that best describes how much you agree or disagree with each statement.

| | Strongly Disagree | Disagree | Undecided | Agree | Strongly Agree |
|------------------------------------------------------------------------------------------------------------|-------------------|----------|-----------|-------|----------------|
| 1. As far as I am concerned, I don't have any problems that need changing. | 1 | 2 | 3 | 4 | 5 |
| 2. I think I might be ready for some self-improvement. | 1 | 2 | 3 | 4 | 5 |
| 3. I am doing something about the problems that had been bothering me. | 1 | 2 | 3 | 4 | 5 |
| 4. It might be worthwhile to work on my problem. | 1 | 2 | 3 | 4 | 5 |
| 5. As far as I am concerned, I don't have any problems that need changing | 1 | 2 | 3 | 4 | 5 |
| 6. I am not the problem one. It doesn't make much sense for me to consider changing. | 1 | 2 | 3 | 4 | 5 |
| 7. I am finally doing some work on my problem. | 1 | 2 | 3 | 4 | 5 |
| 8. I have been thinking that I might want to change something about myself. | 1 | 2 | 3 | 4 | 5 |
| 9. I have been successful in working on my problem, but I'm not sure I can keep up the effort on my own. | 1 | 2 | 3 | 4 | 5 |
| 10. At times my problem is difficult, but I am working on it. | 1 | 2 | 3 | 4 | 5 |
| 11. Trying to change is pretty much a waste of time for me because the problem doesn't have to do with me. | 1 | 2 | 3 | 4 | 5 |
| 12. I'm hoping that I will be able to understand | 1 | 2 | 3 | 4 | 5 |

| | | | | | |
|---------------------------------------------------------------------------------------------------------------------------------------|---|---|---|---|---|
| myself better. | | | | | |
| 13. I guess I have faults, but there is nothing that I really need to change. | 1 | 2 | 3 | 4 | 5 |
| 14. I am really working hard to change. | 1 | 2 | 3 | 4 | 5 |
| 15. I have a problem, and I really think I should work on it. | 1 | 2 | 3 | 4 | 5 |
| 16. I'm not following through with what I had already changed as well as I had hoped, and I want to prevent a relapse of the problem. | 1 | 2 | 3 | 4 | 5 |
| 17. Even though I'm not always successful in changing, I am at least working on my problem. | 1 | 2 | 3 | 4 | 5 |
| 18. I thought once I had resolved the problem I would be free of it, but sometimes I still find myself struggling with it. | 1 | 2 | 3 | 4 | 5 |
| 19. I wish I had more ideas on how to solve my problems. | 1 | 2 | 3 | 4 | 5 |
| 20. I have started working on my problem, but I would like help. | 1 | 2 | 3 | 4 | 5 |
| 21. Maybe someone or something will be able to help me. | 1 | 2 | 3 | 4 | 5 |
| 22. I may need a boost right now to help me maintain the changes I've already made. | 1 | 2 | 3 | 4 | 5 |
| 23. I may be part of the problem, but I don't really think I am. | 1 | 2 | 3 | 4 | 5 |
| 24. I hope that someone will have some good advice for me. | 1 | 2 | 3 | 4 | 5 |
| 25. Anyone can talk about changing; I'm actually doing something about it. | 1 | 2 | 3 | 4 | 5 |
| 26. All this talk about psychology is boring. Why can't people just forget about their problems. | 1 | 2 | 3 | 4 | 5 |
| 27. I'm struggling to improve myself from having a relapse of my problem. | 1 | 2 | 3 | 4 | 5 |
| 28. It is frustrating, but I feel I might be having a recurrence of a problem I thought I had resolved. | 1 | 2 | 3 | 4 | 5 |
| 29. I have worries, but so does the next guy. | 1 | 2 | 3 | 4 | 5 |

| | | | | | |
|------------------------------------------------------------------------------------------------------|---|---|---|---|---|
| 30. I am actively working on my problem. | 1 | 2 | 3 | 4 | 5 |
| 31. I would rather cope with my faults than try to change them. | 1 | 2 | 3 | 4 | 5 |
| 32. After all I had done to try to change my problem, every now and again it comes back to haunt me. | 1 | 2 | 3 | 4 | 5 |

URICA Scoring

1. Obtain the average score per subscale using the following grid:

| Pre-contemplation (PC) | Contemplation (C) | Action (A) | Maintenance (M) |
|--------------------------------------|--------------------------------------|--------------------------------------|--------------------------------------|
| 1. _____ | 2. _____ | 3. _____ | 6. _____ |
| 5. _____ | 8. _____ | 7. _____ | 16. _____ |
| 11. _____ | 12. _____ | 10. _____ | 18. _____ |
| 13. _____ | 15. _____ | 14. _____ | 22. _____ |
| 23. _____ | 19. _____ | 17. _____ | 27. _____ |
| 26. _____ | 21. _____ | 25. _____ | 28. _____ |
| 29. _____ | 24. _____ | 30. _____ | 32. _____ |
| Total _____ divided by 7= Average | Total _____ divided by 7= Average | Total _____ divided by 7= Average | Total _____ divided by 7= Average |

2. Compute the “Readiness for Change” score via the following formula:

$$(\text{Avg C} + \text{Avg A} + \text{Avg M}) - \text{Avg PC}$$

3. Compare the Readiness for Change score to the following group means. Choose the stage whose group average is closest to the computed Readiness Score:

[figure not shown]
| STAGE | GROUP AVG |
|------------------------|-----------------|
| Pre-Contemplation | 9.3 |
| Contemplation | 11.0 |
| Participation (Action) | 12.6 |
| Maintenance | (Not Available) |

Appendix 11

Lack of transport of PF-5190457 by P-glycoprotein

[name] and [name], Clinical Pharmacokinetics Research Laboratory, University of Rhode Island

The Pfizer original investigator's brochure indicate that PF-5190457 is transported by P-glycoprotein 1 (permeability glycoprotein, abbreviated as P-gp or Pgp) also known as multidrug resistance protein 1 (MDR1). The basis of their experiments was in MDCK cell line and P-gp knockout mice. To establish whether or not PF-5190457 is transported by human P-gp, we have conducted in vitro transport experiments in normal Caco-2 cells and Caco-2 cells over expressing P-glycoprotein. Caco-2 cells was derived from colon of human Caucasian colon adenocarcinoma. In order to induce P-gp, Caco-2 cells were treated with an anticancer agent, vinblastine until a resistance strain of the cells were developed. Immunohistochemistry of vinblastine treated cells is shown in Figure 1 were green fluorescence indicate the increased expression of P-gp.

P-gp induced Caco-2 cells, PN 56

Normal Caco-2 cells, PN 56

Figure 1. The higher expression of P-gp transporter on the membrane of P-gp induced cells compare to partial expression of the same transporter in normal Caco-2 cells has been confirmed using immunofluorescent imaging of cells. (Magnification $\times 20$).

The vinblastine treated cells were then functionally evaluated by the use of Calcine AM assay. This assay is a well-established test for evaluating the functional activity of P-gp. The P-gp activity in induced cells were 2-fold higher than normal Caco-2 cells (Figure 2). Inhibitors of P-gp (verapamil and cyclosporine) reduced fluorescence intensity of calcine AM assay in a dose dependent manner while these inhibitors had no influence on normal Caco-2 cells (Figure 2).

[figure not shown]

Figure 2. The fluorescent yield of calcein measured for normal and P-gp induced Caco-2 cells in the presence of verapamil and cyclosporine A (P-gp inhibitors). Results show that by increasing the concentration of inhibitor in P-gp induced cells the fluorescent yield was increased, while there is no significant change for normal cells. The plot shows that the functional activity of P-gp at baseline (no inhibitor present) in transporter-induced cells was more than 2 times higher than that in normal cell line.

Then transport studies of PF-5190457 was carried out in both normal and P-gp induced cells lines. PF-5190457 transport across P-gp induced Caco-2 cells was carried out by adding the drug (5 µg/mL) to apical (A) and basolateral (B) sides of normal and P-gp induced cells. The PF-57 transport was done for 4 h and results obtained from three independent tests and reported as Mean±SD. UR and ER were calculated <2 which means that PF-5190457 neither is actively uptake nor effluxed by P-gp (Table 1).

Table 1. transport of PF-5190457 in normal Caco-2 and P-gp induced cells.

| Parameters | Normal cells | |
|-------------------------------------------|--------------|------------|
| | A-B | B-A |
| Flux | 0.07±0.01 | 0.03±0.001 |
| P _{app} (×10 ⁻⁶ cm/s) | 3.74±0.31 | 4.36±0.28 |
| UR | 0.86±0.04 | |
| ER | 1.17±0.05 | |

| Parameters | P-gp induced cells | |
|-------------------------------------------|--------------------|------------|
| | A-B | B-A |
| Flux | 0.06±0.01 | 0.02±0.001 |
| P _{app} (×10 ⁻⁶ cm/s) | 3.53±0.76 | 3.52±0.14 |
| UR | 1.02±0.26 | |
| ER | 1.01±0.25 | |

We have then investigated the effect of ethanol exposure on the possible transport of PF-5190457 by P-gp. PF-5190457 transport across P-gp induced Caco-2 cells was carried out by adding the drug (5 µg/mL) to apical (A) and basolateral (B) sides of cells. The drug transport was assessed after 24 h treatment in the absence (0 mM) and presence of EtOH (25-500 mM). Cells were kept in the saturated EtOH chambers with the corresponding EtOH concentration at the humidified incubator (37 °C, 95% air+5% CO₂) and by the end of 1 day treatment, the PF-5190457 transport experiments were performed for 4 h.

The results obtained from three independent tests and reported as Mean ± SD. Statistical significance between mean values was calculated using ANOVA (Sigma plot version 12). Probability values <0.05 were considered significant. Table 2 shows the result of this experiment. No statistically significant difference was observed for B-A transport of PF-5190457 in the absence and presence of 200 µl verapamil (P-gp inhibitor) for EtOH treated cells compare to negative control. Based on the results, while Efflux ration <2 of PF-5190457 indicated that this compound is not a P-gp substrate.

Table 2. PF-5190457 transport across P-gp induced Caco-2 cells in the presence of different EtOH concentrations

| Parameters | EtOH concentration (mM) | A-B | | B-A | |
|------------------------------------------------|-------------------------|-------------------|----------------|-------------------|----------------|
| | | Without Verapamil | With Verapamil | Without Verapamil | With Verapamil |
| P_{app} (×10⁻⁶ cm/s) | 0 | 0.82±0.08* | 0.34±0.06** | 0.49±0.03*** | 0.32±0.08**** |
| | 25 | 1.00±0.33 | 0.81±0.29 | 0.5±0.15 | 0.41±0.02 |
| | 50 | 1.28±0.37 | 1.16±0.05 | 0.42±0.07 | 0.37±0.06 |
| | 100 | 1.59±0.08 | 1.45±0.25 | 0.37±0.06 | 0.45±0.05 |
| | 500 | 1.50±0.08* | 1.28±0.01** | 0.52±0.06*** | 0.38±0.15**** |
| UR | 0 | 1.69±0.27 | 1.17±0.58 | | |
| | 25 | 2.08±0.86 | 2±0.64 | | |
| | 50 | 3.06±0.66 | 3.48±0.11 | | |
| | 100 | 4.4±0.75 | 3.13±0.19 | | |
| | 500 | 2.9±0.15 | 4.6±2.32 | | |
| ER | 0 | 0.6±0.1 | 0.98±0.49 | | |
| | 25 | 0.53±0.18 | 0.53±0.17 | | |
| | 50 | 0.34±0.07 | 0.29±0.01 | | |
| | 100 | 0.23±0.04 | 0.32±0.02 | | |
| | 500 | 0.35±0.02 | 0.25±0.13 | | |

* P-value: 0.01, **P-value: 0.079, *** P-value: 0.22, **** P-value: 0.5

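### URICA scoring key: printed item 6, a denial of any need to change, is averaged into Maintenance without reversal, so agreeing with it raises Readiness; item 5 repeats item 1

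*Combined protocol and SAP*

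**What the plan says.** Appendix 10 prints the URICA as 32 statements answered from 1 (strongly disagree) to 5 (strongly agree). Item 6 opens "I am not the problem one" and its second sentence says it does not "make much sense for me to consider changing". Item 5, which begins "5. As far as I am concerned", repeats the sentence printed as item 1.

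The scoring page that follows assigns seven items to each of four subscales:

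- Pre-contemplation (PC): 1, 5, 11, 13, 23, 26, 29
- Contemplation (C): 2, 8, 12, 15, 19, 21, 24
- Action (A): 3, 7, 10, 14, 17, 25, 30
- Maintenance (M): 6, 16, 18, 22, 27, 28, 32

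Each column total is divided by 7. Readiness is (C + A + M) − PC, and the respondent takes the stage whose printed group mean is nearest: 9.3, 11.0 or 12.6. No step reverses any item.

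Section 11.1 describes the URICA by its four subscales. Section 11.2 schedules it at baseline and after Visits 2 and 4 of each counselling phase. Section D makes the outpatient comparison a tertiary aim, and the Précis makes that phase optional.

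**The concern.** The content of item 6 does not fit the column that scores it. The other Maintenance items are about holding on to change already made: item 16 ends "and I want to prevent a relapse of the problem" and item 22 reads "I may need a boost right now to help me maintain the changes". Denials like item 6 sit in Pre-contemplation: item 11 ("Trying to change is pretty much a waste of time for me because the problem"), item 13 ("I guess I have faults, but there is nothing that I really need to change"), item 23 ("23. I may be part of the problem") and item 1. Pre-contemplation is subtracted from Readiness, whereas Maintenance is added.

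A participant who becomes more willing to change should agree less with item 6, and under the printed key that lowers Maintenance and Readiness. The error works against detecting the improvement that the outpatient intervention is meant to produce. It applies whether the subscales or the Readiness score is reported, because item 6 is inside the Maintenance average in both cases.

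At stake is the interpretation of one secondary-level scale within the tertiary aim, not the drug comparison.

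**Working it through.** **Inputs.** All come from Appendix 10: responses coded 1 to 5, the item grid, the divisor of 7, the Readiness formula, and the stage means 9.3, 11.0 and 12.6.

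**Is the grid intact?** Each column holds exactly 7 items, matching the divisor. That accounts for 28 of the 32 items; items 4, 9, 20 and 31 are not scored. Item numbers appear both beside the statements and inside the grid cells, so a shifted table column would not explain the mismatch.

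**Effect of item 6.** Let x be the answer to item 6 and m the mean of items 16, 18, 22, 27, 28 and 32.

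- Printed Maintenance = (6m + x)/7
- Printed Readiness = C + A + (6m + x)/7 − PC
- Per point of x: 1/7 = 0.14 on both scores
- x from 1 to 5: 4/7 = 0.57 on both scores

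The gaps between stage means are 11.0 − 9.3 = 1.7 and 12.6 − 11.0 = 1.6. The full range of item 6 is therefore 0.571/1.7 = 34% and 0.571/1.6 = 36% of a gap.

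**A fully motivated respondent.** Take C = A = 5, PC = 1 and m = 5.

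- Rejecting the denial (x = 1): Maintenance = (30 + 1)/7 = 4.43; Readiness = 5 + 5 + 4.43 − 1 = 13.43
- Endorsing the denial (x = 5): Maintenance = 35/7 = 5.00; Readiness = 14.00

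The maximum score is reached only by strongly agreeing with the denial.

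**A one-point shift toward readiness on every item.** C, A and m rise by 1; the Pre-contemplation items and item 6 fall by 1.

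| Scoring of item 6 | Change in Maintenance | Change in Readiness |
|---|---|---|
| As printed | (6 − 1)/7 = 0.71 | 1 + 1 + 0.71 + 1 = 3.71 |
| Left out of Maintenance | 1.00 | 1 + 1 + 1 + 1 = 4.00 |
| Left out, and counted in PC in place of item 5 | 1.00 | 4.00 |
| Kept in Maintenance, reversed (6 − x) | (6 + 1)/7 = 1.00 | 4.00 |

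The last three rows are illustrations; the documents do not show which was intended. All three give the same comparator, so the loss does not depend on that choice: 1.00 − 0.71 = 0.29 raw points on either score, which is 29% of the Maintenance change and 0.29/4.00 = 7% of the Readiness change.

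**Error for one respondent.** Printed minus six-item Maintenance = (6m + x)/7 − m = (x − m)/7, which lies between −4/7 and +4/7.

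**Stage assignment.** In three trial profiles (motivated, denying, mid-scale), changing item 6 alone did not alter the nearest stage. It could do so for scores near the midpoints, (9.3 + 11.0)/2 = 10.15 and (11.0 + 12.6)/2 = 11.8.

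**Item 5.** One statement fills two of the seven Pre-contemplation places, a weight of 2/7 = 29%. This has no shown effect on the score by itself.

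**Exposure.** 1 baseline + 2 (motivational interviewing phase) + 2 (supportive counselling phase) = up to 5 completions per participant.

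**The case against.** The strongest case is that this is a proofreading error on which no stated analysis depends. Section H names no URICA, Readiness or stage endpoint. Section 11.1 presents a different scale, the SOCRATES, as the overall measure of motivation to abstain, and mentions the URICA last. Section K allows questionnaires on paper or by computer, so participants may have completed a correct form. Item 5 could be a text-reading artefact, since one SIMS item in Appendix 5 is also printed twice. The 0.57 figure needs one person to cross the whole response range on one item with all else fixed. The counselling comparison is a within-person crossover, so a constant offset cancels. The documents do not show whether the item text or the key is at fault. Finally, the title page dates this version August 2021 and records withdrawal of the IND that month, so a corrected form may find little use.

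Much of this stands, and it limits the weight of the point: the reach is small, the cause is unknown, and so is the form actually used. It does not remove the point. Anyone who follows the printed scoring steps obtains a contribution with the wrong sign. A constant offset cancels in the crossover, but a change in item 6 between assessments does not, and change is what the repeated administrations are meant to capture. Item 5 carries its own number and lacks the final full stop of item 1, which favours a source misprint, though extraction error is not excluded. The timing matters little because a scoring rule can be applied to data already collected.

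**Conclusion.** The concern holds. The printed form and key contradict each other, and the key as written rewards agreement with a denial of any need to change: 0.14 per point and at most 0.57 on both Maintenance and Readiness. A uniform one-point improvement is understated by 0.29 on each.

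These are raw-score figures and assume that the printed form and key are the ones used. The effect on standardised contrasts, or on how many participants would be placed in a different stage, cannot be determined, because the documents give no standard deviations or item correlations. Confidence is high for the mismatch and its direction. The intended wording of items 5 and 6 is not established.

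This is a minor point to consider, confined to one scale in an optional tertiary phase. The primary and secondary outcomes are unaffected.

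**What to change.** Before any URICA scoring:

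1. Check the form and the key against the source instrument, correct items 5 and 6 accordingly, and establish which form participants completed.
2. If the misprinted form was used, do not score printed item 6 as Maintenance. Average Maintenance over items 16, 18, 22, 27, 28 and 32, dividing by 6. This is safe whether the text or the key is wrong.
3. Only if the source check confirms it, count printed item 6 in Pre-contemplation in place of the duplicate item 5.
4. Record the rule, and report stage labels as approximate or leave them out.

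The cost is a source check, a corrected form and a short written scoring rule. For data already collected on the misprinted form, the downside is that Maintenance rests on six items instead of seven.
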